#### 15.1.2. MISSING DATA AND OUTLIER METHODS FOR MAIN EFFICACY VARIABLE

All analyses of main efficacy variables will be based on available data. No missing data will be imputed and no outlier will be excluded.

For the sensitive analysis to main efficacy analysis, missing data for DAS28-CRP prior to Week 24 will be imputed and outlier will be handled as described in Section 15.1.4.

If there is any doubt of outlier, a box plot will be used for detecting potential outliers among all subjects, i.e. values higher than  $Q3+1.5 \times IQR$  or lower than  $Q1-1.5 \times IQR$  ( $Q1=25^{th}$  quartile,  $Q3=75^{th}$  quartile,  $IQR=Q3-Q1$ ). The potential outliers among all subjects will be reviewed by medical and be confirmed during blinded data review meeting and prior to database lock and unblinding. If there are any confirmed outliers, then analysis will be performed with and without the outlier(s) to see how the outliers affect study results as sensitivity analysis after unblinding. If there is no confirmed outlier, then box plot and the sensitivity analysis will not be performed after unblinding for final analysis.

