#### **Other Efficacy Endpoints**

- Change from Baseline in DAS28 at Weeks 8, 16, 36, and 52
- ACR20 response rates at Weeks 8, 16, 24, 36, and 52
- ACR50 response rates and ACR70 response rates at Weeks 8, 16, 24, 36, and 52
- Individual components of the ACR improvement criteria on Day 1 and at Weeks 8, 16, 24, 36, and 52
  - Swollen and tender joint count (the 66/68 joint count system)
  - Patient's assessment of pain (assessed on 1 to 100 mm Visual Analogue Scale [VAS])
  - Physician's global assessment of disease activity (assessed on 1 to 100 mm VAS)

- Patient's global assessment of disease activity (assessed on 1 to 100 mm VAS)
- Patient's assessment of disability (Health Assessment Questionnaire-Disability Index [HAQ-DI])
- CRP level
- Change from Baseline DAS28-CRP at Weeks 8, 16, 24, 36, and 52
- Major clinical response (continuous ACR70 for at least 24 weeks)
- Clinical remission (defined by SDAI < 3.3) at Weeks 8, 16, 24, 36, and 52
- Proportion of patients with European League Against Rheumatism (EULAR) response (good response, moderate response or no response) at Weeks 8, 16, 24, 36, and 52

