## 6 STATISTICS

### 6.1 Sample Size

The PK parameters reported from a recent study with rituximab in patients with RA revealed a percentage coefficient of variation (CV%) ranging from 26.3% for  $C_{\max}$  to 37.3% for  $AUC_{0-\infty}$ .

When the evaluable sample size in each group is 84, a three group design will have 81% power to reject both the null hypothesis that the ratio of test to standard geometrics means is below 0.800, and the null hypothesis that the ratio of test to standard geometrics means is above 1.250 (i.e., that the test and standard are not equivalent), in favor of the alternative hypothesis, that the means of the two groups are equivalent, assuming that the expected ratio of means is 1.000, that data will be analyzed in the log scale using analysis of variance (ANOVA) and that each one sided test is made at the 5% level. Each of the 15 hypotheses tests (five co-primary endpoints  $\times$  three pairwise comparisons (i.e., SAIT101 vs. MabThera®, SAIT101 vs. Rituxan®, MabThera® vs. Rituxan®)) are powered at 98% to 99.0% to yield 81% study-wide power.

Approximately 282 patients (94 patients per group) will be randomized in order to yield a minimum of 84 patients per group to account for a presumed 10% withdrawal.

This 94 patients in SAIT101 group and MabThera® group will provide 96% probability of declaring the equivalence in FAS with each one sided test at the 2.5% level, accounting for a presumed 1.0 standard deviation of DAS28 from the REFLEX study, and the equivalence margin of -0.6 to 0.6 chosen as the half of a clinical meaningful improvement of 1.2 in DAS28. Considering 18% withdraw from the REFLEX study, approximately 77 patients per group will provide approximately 91% probability of declaring the equivalence in the PP set with the same above assumption.

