#### **6.4 Efficacy Analysis**

The continuous efficacy endpoint will be analyzed using Analysis of Covariance (ANCOVA) using treatment (SAIT101 and MabThera®) as model factor and Baseline DAS28 as covariate. The Difference between SAIT101 and MabThera® in DAS28 change from Baseline at Week 24 and the associated two-sided 95% CI will be determined.

Equivalence will be concluded if the 95% CI for the mean difference for main efficacy endpoint is completely contained with the equivalence margin of -0.6 to 0.6. Both of the per protocol (PP) set and full analysis set (FAS) will be considered as the efficacy analysis population and the equivalence will be concluded only if the analyses of both PP set and FAS meet the equivalence criteria defined above. No missing data will be imputed for the efficacy analyses in FAS. The possibility of a treatment-by-baseline interaction may be explored as exploratory analyses. In addition, sensitivity analyses will be performed to assess the effect of missing Week 24 data and detailed in the SAP.

Binary endpoints will be analyzed as for the proportion of patients achieving an ACR20 response at Week 24. Two-sided 95% CI for the difference between SAIT101 and

MabThera® in the proportion of patients achieving an ACR20 response at Week 24 will be computed using the Wilson score method.

All statistical comparisons for the secondary efficacy variables will be made using two sided tests at the 0.05 significance level. The 95% CIs of the difference between SAIT101 and MabThera® will be computed.

All efficacy endpoints will be analyzed on the both PP set and FAS.

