### 2.3. SAMPLE SIZE CALCULATION

A percentage co-efficient of variation (CV%) ranging from 26.3 to 37.3% for the five co-primary parameters is assumed for this study based on a recent study in RA patients treated with rituximab.

When the evaluable sample size in each group is 84, a three group design will have 81% power to reject both the null hypothesis that the ratio of test to standard geometrics means is below 0.800, and the null hypothesis that the ratio of test to standard geometrics means is above 1.250 (i.e., that the test and standard are not equivalent), in favor of the alternative hypothesis, that the means of the two groups are equivalent, assuming that the expected ratio of means is 1.000, the CV% for the standard is 0.330, that data will be analyzed in the log scale using analysis of variance (ANOVA) and that each one sided test is made at the 5% level. Each of the 15 hypotheses tests (five co-primary endpoints × three pairwise comparisons) are powered at 98% to 99.0% to yield 81% study-wide power.

Approximately 282 patients (94 patients per group) will be randomized in order to yield a minimum of 84 patients per group to account for a presumed 10% withdrawal.

These 94 patients in SAIT101 group and MabThera® group will provide 96% probability of declaring the equivalence in FAS with each one-sided test at the 2.5% level, accounting for a presumed 1.0 standard deviation (SD) of DAS28 from the REFLEX study, and the equivalence margin of -0.6 to 0.6 chosen as the half of a clinical meaningful improvement of 1.2 in DAS28. Considering 18% withdrawal from the REFLEX study, approximately 77 patients per group will provide approximately 91% probability of declaring the equivalence in the Per Protocol (PP) set.

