#### 4.5. PER PROTOCOL SET [PP]

The Per Protocol Set (PP) consists of all RAN patients who received at least both infusions of study drug in Part A and continued study assessments up to Week 24. Patients with any critical and/or major protocol deviations that affect the efficacy assessments will be assessed for inclusion in the set. Patients may be excluded from the PP set if they did not meet key eligibility criteria, were taking prohibited concomitant medication, received the wrong study drug, or other situations that may affect the efficacy assessments.

Protocol deviations or the situation that leads to exclusion from the PP will be specified and authorized prior to unblinding the treatment arms. Efficacy endpoints will also be summarized on the PP.

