#### 15.1.3. ANALYSIS OF MAIN EFFICACY VARIABLE

The primary objective of this study is to demonstrate equivalence in the SAIT101 and MabThera® in DAS28-CRP change from Baseline at Week 24. The equivalence between the two treatment groups will be declared if the two-sided 95% confidence interval (CI) of the difference in change from baseline in DAS28-CRP between SAIT101 and MabThera® is entirely contained within the equivalence margin of [-0.6, 0.6].

An analysis of co-variance (ANCOVA) model of change from baseline in DAS28-CRP at Week 24 with treatment group as factors and the baseline DAS28-CRP value as a covariate will be used to test the treatment difference of SAIT101 versus MabThera®. Least squares mean (LSM), standard error and two-sided 95% confidence interval for change from baseline will be reported for each treatment group. For the treatment difference, the LSM difference, standard error, and two-sided 95% confidence interval will be reported for both FAS and PP.

---

Document:	\\ieedc-vnasc01\Biosdata\Archigen\SAIT101\YWA21301\Biostatistics\Documentation\SAP	
Author:		Version Number: V2.0
		Version Date: 13Feb2019

Template No: CS\_TP\_BS016 Revision 4  
Effective Date: 01Apr2016

Reference: CS\_WI\_BS005

Value of DAS28-CRP and its change from baseline will also be listed.

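### The deciding efficacy analysis uses only patients with a Week 24 DAS28-CRP and ignores the Week 8 and 16 scores of those who leave; if poor responders are the ones missing, the estimate drifts toward equivalence

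*SAP*

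**What the plan says.** SAP 4.3 and Protocol 6.2.1.3 define the FAS as all randomized patients. The deciding model in SAP 15.1.3 is: "An analysis of co-variance (ANCOVA) model of change from baseline in DAS28-CRP at Week 24 with treatment group as factors", with baseline DAS28-CRP as the only covariate. SAP 15.1.2 restricts it to observed scores: "All analyses of main efficacy variables will be based on available data. No missing data will be imputed". Protocol 6.4 agrees: "No missing data will be imputed for the efficacy analyses in FAS". Under SAP 15.1.1 a DAS28-CRP score is missing if any of its components is missing.

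Protocol 6.4 concludes equivalence only if FAS and PP both meet the margin. SAP 4.5 limits PP to randomized patients who "received at least both infusions of study drug in Part A and continued study assessments up to Week 24".

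Earlier scores are collected. Protocol 2.3.2 lists "Change from Baseline in DAS28 at Weeks 8, 16, 36, and 52" among the other efficacy endpoints, and SAP 15.2.1 analyzes DAS28-CRP at those visits. For missing Week 24 scores, SAP 15.1.4 plans four sensitivity analyses: LOCF, BOCF, BOCF for treatment-related reasons only, and BOCF for those reasons combined with missing-at-random multiple imputation for the rest.

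**The concern.** Although it is labelled FAS, the deciding analysis compares the products among patients who reach Week 24 with a complete score. It is unbiased only if missing Week 24 is unrelated to response once baseline is taken into account. Early response is known for anyone who leaves after Week 8 or 16, yet the model sets it aside.

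In an equivalence trial the direction of this error matters. If one product is worse and poor responders leave, more patients are removed from the worse arm. The remaining patients look more alike, and a false claim of equivalence becomes easier. Requiring PP as well gives no protection, because PP also needs assessments to Week 24.

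**Working it through.** **1. The plan's own power figures.** Inputs from SAP 2.3: SD 1.0, "the equivalence margin of -0.6 to 0.6", "with each one-sided test at the 2.5% level", 94 per arm (FAS) and 77 per arm (PP). Assumed true difference: 0.

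Power = 2Φ(0.6 / √(2/n) − 1.96) − 1

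- n = 94: √(2/94) = 0.1459; 0.6/0.1459 = 4.113; 2Φ(2.153) − 1 = 96.9% (stated 96%).
- n = 77: √(2/77) = 0.1612; 0.6/0.1612 = 3.723; 2Φ(1.763) − 1 = 92.2% (stated about 91%).

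Both reproduce closely. The PP size is 94 × 0.82 = 77.08; in Protocol 6.1, "Considering 18% withdraw from the REFLEX study, approximately 77 patients per group". The 96% therefore counts all 94 patients per arm as scored at Week 24. With no imputation, if 18% really lacked that score, FAS would also have about 77 per arm and about 92% power.

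**2. Why the estimate shrinks.** Let the SD be 1 at each visit and ρ the correlation between the Week 16 and Week 24 changes. If leaving depends on the Week 16 change, then in each arm

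mean(Week 24 | stayed) = mean(Week 24) − ρt,

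where t is the amount by which the Week 16 mean falls when the leavers are removed. The available-data difference is the true difference minus ρ(t_worse − t_better). The worse arm loses more patients from its poor end, so t_worse > t_better and the difference shrinks. A likelihood model that keeps the earlier scores instead estimates

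δ24 = β_treatment + β_16 × δ16,

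with the β terms taken from patients who have both scores and δ16 from everyone scored at Week 16.

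**3. Size.** Simulated with 94 per arm, SD 1.0, a true difference of 0.6 and baseline as a covariate. These inputs are assumptions, not in the documents: logistic dropout on the Week 16 change, log-odds 0.5 to 2.0 per SD, and 5% to 18% missing.

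| Analysis | Mean estimate of a true 0.6 | False equivalence (nominal 2.5%) |
|---|---|---|
| Week 24 ANCOVA, available data | 0.53-0.60 | about 2.4-6.4% |
| Likelihood model adding Week 16 | 0.60 | 2.0-2.7% |

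A separate run shows the gradient at 18% missing. It assumed a baseline-change correlation of 0.4, an adjacent-visit correlation of 0.7, and 90% of the effect present by Week 16.

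| Log-odds per SD | ANCOVA estimate | False equivalence |
|---|---|---|
| 1.0 | 0.57 | 4.0% |
| 1.5 | 0.55 | 5.7% |
| 2.0 | 0.53 | 7.1% |

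The likelihood model gave 0.60 and 2.5-2.7% in these cases. The two runs differ a little in the worst corner (6.4% and 7.1%), so that corner should be read as roughly 6-7%.

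**4. Weak or no dependence.** At log-odds 0.5 per SD the bias is about 1-3%. In a run without the baseline covariate, false equivalence at that slope was 2.6-3.2%. With dropout at random the estimate is 0.60 and the rate about 2.5%.

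**5. Power.** At a true difference of 0, with log-odds 1.5, power is 97.1% for the ANCOVA and 97.3% for the likelihood model, so nothing is lost.

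**6. Dropout driven by the unseen Week 24 score.** With baseline adjusted, at 18% missing and log-odds 1.0, the ANCOVA averages 0.545 with 5.4% false equivalence. The likelihood model averages 0.567 with 3.9%, so the correction is only partial.

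**The case against.** The strongest reply is that the design works against the mechanism. Patients who stop treatment, including those given rescue, attend all visits to Week 52 (Protocol 3.2.6 and 3.6.6, SAP 2.2). Lack of efficacy is a reason to stop treatment (Protocol 3.7.3); leaving the study is limited to withdrawn consent or loss to follow-up (Protocol 3.4.4). Eligibility for a second course is judged at Week 24, which gives poor responders a reason to attend. This stands, and it limits the likely size.

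A reader might take 18% as the plan's forecast of missing Week 24 scores. It is not: it is another study's withdrawal rate, used to size PP, and the 10% allowance sizes the PK-evaluable groups. Neither is tied to response.

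A reader might also infer that the plan never uses the early scores. LOCF uses them for every withdrawn patient with a post-baseline value, and in simulations of this mechanism it showed no shrinkage (0.60-0.635 for a true 0.6). That good showing partly reflects the equal differences assumed at Weeks 16 and 24. The multiple imputation also uses previous-visit components. What remains is that no planned analysis applies missing at random to all withdrawals, and none of the sensitivity analyses decides equivalence. BOCF for everyone is no safe check either: under random 18% dropout it turns 0.6 into 0.82 × 0.6 = 0.49.

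Finally, the protocol's primary objective is PK and efficacy is secondary. That is correct and lowers the weight of the point, although SAP 15.1.3 words the DAS28-CRP comparison as the study's primary objective.

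**Conclusion.** The point holds as a conditional weakness in the deciding analysis; the plan's arithmetic is not in error. FAS and PP share a selection on having reached Week 24, and if that selection depends on response, the bias favours equivalence. With baseline adjusted, a true difference at the margin and dropout driven by Week 16, the estimate is about 0.53-0.60 and false equivalence about 2.4-6.4% over 5-18% missing. It is negligible where dropout is weakly related to response.

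Much larger rates can be produced: up to 12.8% when dropout follows Week 16, and 30.8% when it follows the unseen Week 24 score. Those need log-odds of 4 per SD, 18% missing and no baseline covariate. Nothing in the documents supports such dropout, so they should not be read as the expected risk. All sizes rest on assumed correlations and dropout models; the direction was the same in every scenario where poor response raised the chance of leaving. The change is worth making because it is cheap, not because serious bias is likely.

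**What to change.** Before unblinding, make the deciding FAS analysis in SAP 15.1.3 a mixed model for repeated measures on change from baseline in DAS28-CRP at Weeks 8, 16 and 24. Include treatment, visit, treatment-by-visit, baseline and baseline-by-visit, with an unstructured within-patient covariance. Judge the Week 24 SAIT101 minus MabThera 95% CI against −0.6 to 0.6, and keep the ANCOVA as supportive. The model imputes nothing, so the no-imputation statements can stand.

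PP can stay as it is. Both sets must pass, so the chance of a false claim cannot exceed the FAS rate, which the new model holds near nominal under missing at random.

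Add a delta-adjusted check that starts from non-equivalence: shift the imputed Week 24 scores of missing patients in one arm by up to 0.6, in each direction, and see whether the conclusion survives. At 18% missing the largest shift moves the estimate by 0.18 × 0.6 = 0.108; at 5% missing, by 0.05 × 0.6 = 0.03.

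The cost is one extra model, one sensitivity analysis, an entry in SAP 2.6 and alignment of Protocol 6.4, which names ANCOVA. Protocol 13 treats permanent protocol changes as amendments, so that alignment is more than an edit to the SAP. No new data, visits or patients are needed. Patients with no post-baseline score still contribute nothing, and dropout driven by the unseen Week 24 score is corrected only in part.

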#### 15.1.3. ANALYSIS OF MAIN EFFICACY VARIABLE

The primary objective of this study is to demonstrate equivalence in the SAIT101 and MabThera® in DAS28-CRP change from Baseline at Week 24. The equivalence between the two treatment groups will be declared if the two-sided 95% confidence interval (CI) of the difference in change from baseline in DAS28-CRP between SAIT101 and MabThera® is entirely contained within the equivalence margin of [-0.6, 0.6].

An analysis of co-variance (ANCOVA) model of change from baseline in DAS28-CRP at Week 24 with treatment group as factors and the baseline DAS28-CRP value as a covariate will be used to test the treatment difference of SAIT101 versus MabThera®. Least squares mean (LSM), standard error and two-sided 95% confidence interval for change from baseline will be reported for each treatment group. For the treatment difference, the LSM difference, standard error, and two-sided 95% confidence interval will be reported for both FAS and PP.

---

Document:	\\ieedc-vnasc01\Biosdata\Archigen\SAIT101\YWA21301\Biostatistics\Documentation\SAP	
Author:		Version Number: V2.0
		Version Date: 13Feb2019

Template No: CS\_TP\_BS016 Revision 4  
Effective Date: 01Apr2016

Reference: CS\_WI\_BS005

Value of DAS28-CRP and its change from baseline will also be listed.

#### 15.1.4. SENSITIVITY ANALYSIS OF MAIN EFFICACY VARIABLE

If there is any statistical outlier, a sensitivity analysis will be performed for the main efficacy without outlier(s) to see whether the outlier(s) affect study results.

All sensitivity analyses below will be performed for the main efficacy variable of DAS28-CRP change from baseline at Week 24.

A sensitivity analysis will be performed for the main efficacy with the addition of the following covariates to the statistical model: Region (EU, US, Other), age, sex, ADA status at baseline (positive, negative), body weight at baseline, and baseline DAS28-CRP based on the FAS and PP. Besides, another sensitivity analysis will be performed for main efficacy with the treatment interaction term and baseline DAS28-CRP based on the FAS and PP.

The same analysis with the main efficacy analysis will be repeated for the PP and FAS with imputed DAS28-CRP for those of subjects withdrew before 24 weeks to explore the robustness of the results. The missing data imputation methods in detail are as follows:

- Last Observation Carried Forward (LOCF) approach will be applied. For all patients withdrawn from study for any reason, the last non-missing observation before withdrawal will be carried forward to the subsequent endpoint visit for evaluation. Enrolled patients without at least one post-baseline observation will not be included for evaluation.
- Baseline-observation-carried-forward (BOCF) approach will be applied regardless of any withdrawal reason. Enrolled patients without at least one baseline observation will not be included for evaluation.
- For patients with missing DAS28-CRP at Week 24 due to treatment-related reasons, i.e. treatment discontinuation for receiving rescue therapy OR adverse events OR lack of efficacy before Week24, the patients will be considered as DAS28-CRP non-responders at Week 24 and the BOCF approach will be applied. Otherwise, no imputation will be applied.
- For patients with missing DAS28-CRP at Week 24 due to treatment-related reasons, i.e. treatment discontinuation for receiving rescue therapy OR adverse events OR lack of efficacy before Week24, the BOCF approach will be applied. Otherwise, multiple imputation for missing at random approach will be applied. In order to preserve any observed difference between treatment groups, best change will be assumed to be missing at random (MAR). Robustness of the main efficacy conclusion to the missing at random assumption will be evaluated by sensitivity analyses that will take account the reasons for withdrawal.

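### The missing-data sensitivity analyses for DAS28-CRP give only weak support for equivalence, and none is a graded departure from missing-at-random that stresses the ±0.6 margin

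*SAP*

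**What the plan says.** The main efficacy analysis (SAP 15.1.2 and 15.1.3) is an ANCOVA of change in DAS28-CRP at Week 24 on available data, with nothing imputed. Equivalence needs the two-sided 95% CI for SAIT101 minus MabThera to lie within ±0.6, and Protocol 6.4 requires this in both the FAS and the PP set. SAP 2.3 describes "the equivalence margin of -0.6 to 0.6 chosen as the half of a clinical meaningful improvement of 1.2 in DAS28".

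SAP 15.1.4 then repeats the analysis in both sets under four imputation rules:

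1. For withdrawals of any kind, the "Last Observation Carried Forward (LOCF) approach will be applied".
2. For baseline carried forward, the "approach will be applied regardless of any withdrawal reason".
3. BOCF where Week 24 is missing for a treatment-related reason (rescue, adverse event, lack of efficacy), and no imputation otherwise.
4. BOCF for the same treatment-related reasons, and MAR multiple imputation otherwise.

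After the fourth rule the SAP states: "Robustness of the main efficacy conclusion to the missing at random assumption will be evaluated by sensitivity analyses". The sentence goes on to say that these analyses will allow for why patients withdrew. Appendix 4 gives the imputation code (100 imputations). Neither place gives a shift parameter or a tipping point.

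**The concern.** In a superiority trial, an imputation that draws the arms together is conservative. In an equivalence trial it favours the claim. BOCF assigns zero change to dropouts in both arms, so with similar dropout it dilutes any real difference by the proportion missing. LOCF can do the same if the arms were closer together at earlier visits. A sensitivity analysis that tends to favour the conclusion under test adds little when it agrees.

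At stake is how the DAS28-CRP result is read. The PP set requires assessments up to Week 24 (SAP 4.5), so it has little to impute. The imputed FAS analyses are therefore the plan's main check on attrition. If all four agree with the main analysis, a reader may take equivalence as robust to missing data without any analysis having shown how unfavourable the missing values would need to be to overturn it.

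**Working it through.** **Inputs.** From SAP 2.3: margin 0.6; "a presumed 1.0 standard deviation (SD) of DAS28 from the REFLEX study"; tests "with each one-sided test at the 2.5% level"; 94 per arm; withdrawal of 18% (efficacy) and 10% (PK). From Protocol 1.3.2: mean DAS change on rituximab of −1.9. Assumptions: the SD of 1.0 applies to the change score; dropout is completely at random; the baseline covariate is ignored; the reference arm changes by −1.9.

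**Step 1: reproduce the plan's power.** With a true difference of 0 (assumed; the plan does not state it), power = 2Φ(0.6/√(2/n) − 1.96) − 1.
- n = 94: 96.9% (96.7% with the t distribution). Plan: "These 94 patients in SAIT101 group and MabThera® group will provide 96% probability of declaring the equivalence in FAS".
- n = 77 (94 × 0.82 = 77.1): 92.2% (91.8% with t). Plan: "approximately 77 patients per group will provide approximately 91% probability of declaring the equivalence in the Per Protocol (PP) set".

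Both agree to within 2 points, so the inputs are read correctly.

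**Step 2: BOCF with equal dropout d.** Put the true difference at the margin: SAIT101 −1.3, MabThera −1.9. Without bias, equivalence is shown Φ(−1.96) = 2.5% of the time. Under BOCF:
- expected difference = 0.6(1 − d)
- variance per arm = (1 − d) + d(1 − d)μ², where μ is that arm's mean change
- chance of showing equivalence = Φ((0.6 − difference)/SE − 1.96)

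| d | Difference | SE | Shows equivalence |
|---|---|---|---|
| 10% | 0.540 | 0.1556 | 5.8% |
| 18% | 0.492 | 0.1605 | 9.9% |

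For d = 18%: SE = √((1.3528 + 1.0694)/94) = 0.1605, and Φ(0.108/0.1605 − 1.96) = 9.9%.

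**Step 3: LOCF with 18% equal dropout.** Let f be the share of the Week 24 difference already present at the carried-forward visit. Expected difference = 0.6(1 − d + df), with SE = √(2/94) = 0.146.

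| f | Difference | Shows equivalence |
|---|---|---|
| 0 | 0.492 | 11.1% |
| 0.5 | 0.546 | 5.6% |
| 0.75 | 0.573 | 3.8% |
| 1.0 | 0.600 | 2.5% |
| 1.25 | 0.627 | 1.6% |

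The documents give no visit profile, so f is unknown.

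**Step 4: BOCF with unequal dropout** (SAIT101 first).
- True 0, 26% vs 10%: −1.9 × 0.74 − (−1.9 × 0.90) = −1.406 + 1.710 = +0.30. Equivalence is shown only 42% of the time.
- True +0.6, 26% vs 10%: 0.748, shown 0.2% of the time.
- True +0.6, 10% vs 26%: 0.236, shown 61% of the time.
- True +0.6 with 18% on MabThera: the shrinkage is cancelled when SAIT101 dropout is 1 − (0.82 × 1.9 − 0.6)/1.3 = 26%.

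**Step 5: simulation.** 3,000 trials per scenario, dropout completely at random after Week 8 or 16, visit correlations 0.6 to 0.7 (assumed), true difference 0.6.
- BOCF at 18% equal dropout: 9.3% with a growing difference, 9.9% with a constant one.
- LOCF at 18% equal dropout: 4.7% if half the difference is present at Week 8 and 80% at Week 16; 2.3% if it is constant.
- Available-case and MAR imputation, across equal and unequal dropout: 2.3% to 2.8%.

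**Step 6: what a tipping point would show.** With 18% missing and only SAIT101 imputed values shifted, the 95% half-width is about 1.96√(2/77.08) = 0.316. Equivalence is lost at a shift of (0.6 − 0.316)/0.18 ≈ 1.6 DAS28 units if the observed difference is 0, but at (0.4 − 0.316)/0.18 ≈ 0.5 if it is 0.2.

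**The case against.** The best defence has four parts.

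- **The decision rule is untouched.** Equivalence is judged on unimputed FAS and PP data, so these analyses cannot raise the trial's type I error. This stands. A reader might infer that the plan makes a false equivalence claim more likely; the documents do not support that. DAS28 also serves a secondary objective, the primary one being PK.
- **The direction is not fixed.** A reader might infer that LOCF and BOCF always pull the difference toward zero and so cannot test robustness. Steps 3 and 4 show otherwise. BOCF can expose excess dropout on SAIT101, and LOCF is unbiased if the difference is constant. This stands, but it does not make BOCF a good check. With 26% vs 10% dropout a true −0.6 becomes −1.85 + 1.71 = −0.14, and equivalence is shown about 68% of the time in simulation. BOCF responds to dropout imbalance, so neither a pass nor a fail is easy to interpret.
- **The SAP does depart from MAR by reason.** Rules 3 and 4 apply BOCF to treatment-related dropout, as the sentence on withdrawal reasons promises. This stands in part. It is one fixed departure, the same in both arms, and does not show how large a departure the conclusion tolerates.
- **Missing data may be few.** Patients who stop treatment, including those given rescue, are asked to attend all visits to Week 52. This is fair, but the plan itself allows for 18% withdrawal in its efficacy power.

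**Conclusion.** The concern holds in a limited form. With similar dropout in the arms, all-reason BOCF raises the chance that this sensitivity analysis shows equivalence at a true difference of 0.6 from 2.5% to about 6% (10% dropout) or 10% (18%). LOCF does so only when the difference grows over visits, and unequal dropout can send BOCF either way. These sizes rest on SD 1.0 for change, a reference change of −1.9, and dropout completely at random.

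The main conclusion's error rate is unaffected. The gap is in the robustness evidence: none of the four analyses is a graded departure from MAR set against ±0.6, and MAR imputation for all missing values is never run alone, although the SAP says the assumption will be evaluated.

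**What to change.** In SAP 15.1.4, for the FAS, replace all-reason BOCF with a delta-adjusted tipping-point analysis, specified before unblinding:

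1. Multiply impute every missing Week 24 value with the Appendix 4 code. Include the treatment-related dropouts whom rule 4 now sends to BOCF; otherwise the most informative missing values would not be shifted.
2. After DAS28-CRP is computed from the imputed components, shift the imputed SAIT101 values in both directions over a grid that includes ±0.6 and extends until the 95% CI leaves ±0.6. The grid must go beyond ±0.6, because with 18% missing that shift moves the arm difference by only 0.18 × 0.6 ≈ 0.11. A shift of zero gives the stand-alone MAR analysis.
3. Report the smallest shift in each direction that breaks equivalence, so that its plausibility can be judged.
4. Label LOCF and any retained BOCF analysis as supplementary, and report dropout by arm and reason beside them.

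The cost is a few lines added to existing code and one extra table. No new data are needed, and the decision rule does not change.
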